At baseline (prior to vaccination) HIV-negative Ugandans have elevated levels of immune activation (IA) and inflammation: We measured IL-1 β , IL-4, IL-6, IL-10, IL-17A, IL-21, IL-22, IL-23, IL-13, MIP-1 β , TNF, TGF β , and IP10 in plasma samples from Group 1 (Uganda) and Group 3 (Emory) prior to YFV administration. We observed significantly higher levels of TGF β , IL-6, IL-4 and IL-21 and MIP-1 β in Ugandans ($p < 0.001$, $p = 0.03$, $p = 0.004$, $p = 0.001$, and $p = 0.01$ respectively, **Fig. 2A, B**). There were no other statistically significant differences detected. The increase in TGF β in Ugandans is interesting as it is the pro-inflammatory cytokine we have previously associated with TZ fibrosis (13) and may be an important mechanism for LN fibrosis in this population as well. We used immunohistochemistry (IHC) and quantitative image analysis (QIA) to stain for Ki67+ cells in LN as a measure of IA. Ugandans had significantly greater frequency of Ki67+ cells ($p = 0.0019$, **Fig. 2C-E**). Collectively these data demonstrate increased IA and inflammation in HIV negative Ugandans, especially in LN.

[figure not shown]
[figure not shown]

Fig. 2: Increased IA in HIV negative Ugandans. Increased levels of TGF β (A), IL-6 (B), and Ki67+ cells in LN (C) in Ugandans. LN sections stained with Ki67 from U.S. (D) and Ugandan I.

There is increased collagen and decreased CD4 T cells in HIV negative Ugandan LN. We used trichrome staining and QIA to determine the amount of collagen in the TZ in Groups 1 & 2 (Fig. 3 A,B). In Group 1 the mean area of the TZ with collagen was 12.4% (S.D. 3.4%) whereas in Group 2 it was 4.3% (s.d. 2.9%). The amount of TZ collagen in HIV negative Ugandans was similar to the HIV+ people from Minnesota where the mean amount of TZ fibrosis was 12.9% (s.d. 7.4%). The regression analysis, after log transformation of the percent TZ area, showed a significantly increased amount of TZ collagen in Group 1 compared to Group 2 ($p<0.0001$, Fig. 3C). We measured the size of the CD4 population in Group 1 and found the expected (14) significant inverse correlation between TZ collagen and TZ CD4 T cells ($p=0.0322$, Fig. 3D).

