We next measured the FRCn by staining tissues with an antibody against Desmin. In Fig. 4A we show a representative section of the TZ of a LN from the Minnesota group where the Desmin positive TZ area was 22.6% whereas in the Ugandan Group it was 9.5% (range 5.1% - 19.4%, Fig. 4B-C). As expected, there was a direct and significant correlation between the log-transformed area of the TZ that was Desmin positive and the log-transformed size of the TZ CD4 T cell population ($p< 0.0001$, Fig. 4D).

[figure not shown]

[figure not shown]
Fig. 4: The FRCn is depleted in Ugandans. We used QIA to identify TZ Desmin (brown) in HIV negative people in the U.S. (A) and Uganda (B and C) and then used quantitative image analysis to compare the amount of Desmin in the section to the size of the CD4 T cell population in the LN (D) showing the significant and direct relationship.

In summary, people in Uganda have increased IA, inflammation, TZ collagen, damage to the FRCn, and depletion of CD4 T cells. We next gave Group 1 YFV to determine if development of antibodies correlated to any measures of inflammatory damage to the LN.

There were few follicles prior to YFV and no changes in B cell follicles after YFV. We obtained an additional inguinal LN from 20 people in Group 1 and then administered YFV in the thigh opposite the one just biopsied. Ten to fourteen days later we obtained another LN from the same side the vaccine was given. We measured B cell populations, frequency and location of germinal centers, and frequency of Ki67+ cells before and after vaccination. We found few primary or secondary follicles (germinal centers) before vaccination with no significant increase after vaccination. In 63% of participants we saw no follicle formation and in only 3 of the participants did we see an increase in B cell follicles. The mean area of the follicles with B cells prior to vaccination was 25.5% (range 15.7-39.4%) whereas after vaccination it was 24.1% (range 14.0-34.1%, $p=0.34$). There was a significant increase in the frequency of Ki67+ cells ($p=0.002$).

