9 STATISTICAL CONSIDERATIONS

9.1 STATISTICAL HYPOTHESES

- Primary Efficacy Endpoint(s):

Null hypothesis: There is no difference in peak yellow fever antibody titer between individuals from the US and Uganda.

Alternative hypothesis: There is a difference in peak yellow antibody titer.

- Secondary Efficacy Endpoint(s):

Null hypothesis: There is no difference in baseline LN architecture measures (TZ collagen, FRCn, B cell follicles and populations, Tfh cells, and B Cell activating factor) between individuals from the US and Uganda. Alternative hypothesis: There are differences in these measures between the two countries.

Null hypothesis: There is no association between baseline measures of LN architecture and rate of YFV antibody decay. Alternative hypothesis: There are associations between these measures and rate of antibody decay.

Null hypothesis: Principal components of pathseq data are not associated with country of origin.

Alternative hypothesis: Some principal components of pathseq data are be associated with country.

Null hypothesis: There are no difference in helminth infection patterns between the US and Uganda.

Alternative hypothesis: Differences in helminth infections exist between the two countries.

Null hypothesis: Pathseq principal components with strong loadings for infection organisms are not associated with baseline measures of LN architecture. Alternative hypothesis: PC components with strong loadings for infectious organisms are associated with baseline LN architecture measures.

Null hypothesis: Presence of helminth infection is not associated with baseline LN architecture measures. Alternative hypothesis: Presence of helminth infection is associated with baseline LN architecture measures.

Null hypothesis: There is no association between changes in immune function after vaccination and measures of LN architecture. Alternative hypothesis: There is an association between change in immune function and measures of LN architecture.

Null hypothesis: There is no association between CD4, CD8 functional variables and CD4 subsets and peak YFV antibody titers or rate of antibody decay. Alternative hypothesis: There is an

association between CD4, CD8 functional variables and CD4 subsets and peak YFV antibody titers and rate of antibody decay.

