9.4 STATISTICAL ANALYSES

9.4.1 GENERAL APPROACH

Medians and interquartile ranges will be presented for descriptions of continuous data. Percentages will be presented for categorical data.

Counts of cell frequency and QIA endpoints involving the percent area will be log-transformed and linear regression analyses will be conducted where appropriate. If there are no detectable cells or there is no staining detected for a large portion of study participants logistic regression modeling will be conducted, instead, with presence or absence of the measure being the outcome.

Two-sided tests will be conducted for all comparisons. Subjects specific random effects will be included in all mixed effects models and permutation p-values will be presented. To control for multiple comparisons, a cut-off of alpha=0.01 will be used for determining statistical significance of all secondary endpoints.

Measures which have non-zero coefficients in lasso models will be considered to be associated with the outcome. Measures which have non-zero correlation coefficients after applying sparse canonical correlation analysis will be considered to be correlated with the outcome measure.

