9.4.3 ANALYSIS OF THE SECONDARY ENDPOINT(S)

Differences in rate of YFV antibody titer decay will be compared between vaccinated Ugandans and Minnesotans using linear mixed effects regression model with measurement time, country, and the interaction between measurement time and country as predictors. Baseline LN measures (area with collagen, area with desmin staining, frequency and size of B cell follicles, and frequency of Tfh cells) will be compared between the two countries using Mann-Whitney U tests.

We will examine the association between vaccine response over time and baseline LN measures using linear mixed effects models adjusting for measurement time and gender.

To examine differences in infection patterns between the two countries, we will perform principal component analyses on the baseline pathseq data. We will test for differences in infection patterns between Uganda and the US populations using logistic regression with country as the outcome and the scores for each of the first five principal components as predictors. Differences in helminth infections between Ugandans and Minnesotans will be compared using Fisher's exact test.

We will examine the association between infection history and baseline LN architecture by fitting separate linear regression models for each measure of baseline LN architecture with gender and the 5 pathseq principal component scores as predictors. The association between helminth infections and baseline LN architecture measures will be assessed using Mann-Whitney U tests.

To elucidate the role of previous infections on inflammation and activation we will use sparse canonical correlation analysis (Reference: Witten, D., Tibshirani, R., & Hastie, T. (2009). A penalized matrix decomposition, with applications to sparse principal components and canonical correlation analysis. *Biostatistics*, 10(3), 515-534.) to identify sets of organismal sequences correlated with baseline measures of systemic and lymphatic inflammation (plasma cytokines, frequency of TGF β + and TNF+ cells in lymphoid tissues) and immune activation (Ki67+ and CD69 + cells). The association between helminth infection and measures of inflammation and activation be assessed using a logistic lasso regression model. Measures which have non-zero coefficients in the model will be considered associated with helminth infection.

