The association between change in measures of CD8 function (IFN γ , TNF α , and IL-2) after vaccination and measures of LN architecture will be examined by fitting mixed effects linear models using area with collagen staining, area with desmin staining, and measurement time and gender as predictors.

The association between immune function after vaccination and measures of inflammation and activation will be assessed using separate lasso regression for each measure of immune function (antigen specific CD4, CD8 function measures, and CD4 and CD8 subpopulations). Inflammation and activation measures which have non-zero coefficients in the model will be considered predictive of immune function.

We will examine the impact of measures of immune function on YFV response using separate mixed effects linear models with gender, measurement time and measures of immune function (antigen specific CD4, CD8 functional variables, or CD4 and CD8 subpopulations) as predictors. Similar models will be fit for YF specific IgM, IgG1, IgG2, IgG3 and IgG4 responses.

The impact of vaccination on measures of inflammation and activation be assessed using mixed effects repeated measures model with gender, measurement time, and vaccination status as predictors. To assess the impact of vaccination on CD4 and CD8 cells in LT similar models will be fit, but only gender and vaccination status (measurement taken before or after vaccination) will be used as predictors.

Missing data will not be imputed and a significance level of 0.01 will be used for secondary analyses due to the large number of hypotheses to be tested. The results from all of these investigations will be reported so that the reader can assess the effect of multiple hypothesis testing.

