9.4.9 EXPLORATORY ANALYSES

The association between change in the CD4 and CD8 T cell populations after vaccination and measures of LN architecture will be examined by fitting mixed effects linear models estimating T cells populations using area with collagen staining, area with desmin staining, and measurement time and gender as predictors.

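### The models for T-cell change after vaccination have no lymph-node-by-vaccination term, so Section 9.4.9 (and 9.4.3, if its outcome is the repeated level) tests association with average T-cell level

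*Combined protocol and SAP*

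**What the plan says.** Section 9.1 gives the null hypothesis: "There is no association between changes in immune function after vaccination and measures of LN architecture".

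Two models address change against LN architecture.

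- Section 9.4.3, secondary: change in CD8 function (IFN-gamma, TNF-alpha, IL-2) is to be "examined by fitting mixed effects linear models using area with collagen staining, area with desmin staining, and measurement time and gender as predictors". The outcome variable is not named.
- Section 9.4.9, exploratory: change in CD4 and CD8 populations is to be studied with "mixed effects linear models estimating T cells populations using area with collagen staining, area with desmin staining, and measurement time and gender as predictors". Here the outcome is the population itself.

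Neither model has a product of an LN measure with time or vaccination status, and neither adjusts for the pre-vaccination value. Elsewhere in 9.4.3 the titer-decay model does list such a term: "measurement time, country, and the interaction between measurement time and country as predictors". Section 9.4.1 adds that "Subjects specific random effects will be included in all mixed effects models and permutation p-values will be presented", and sets a 0.01 cut-off for secondary endpoints.

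Section 2.2 reports two links in the sponsor's earlier data: a "significant inverse correlation between TZ collagen and TZ CD4 T cells" (p=0.0322, Group 1), and a "direct and significant correlation between the log-transformed area of the TZ that was Desmin positive and the log-transformed size of the TZ" CD4 population (p<0.0001). Section 4.1 plans one LN biopsy before vaccination and one three weeks after.

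**The concern.** Both models are introduced as tests of change, but main effects alone cannot separate change from level. If LN damage already goes with fewer T cells before any vaccine is given, the LN coefficient can reach significance with no relation to the vaccine. A result labelled as association with change after vaccination would then feed the trial's mechanistic argument. The error also runs the other way. A real association with change is diluted, and it can be cancelled if its sign is opposite to that of the baseline association.

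**Working it through.** **Starting point.** The plan gives no power or error rate for these models. Its only such figure, over 85% for the primary titer comparison (30 vs 16, difference 1 log, SD 1 log, two-sided 0.05), reproduces as 0.884 on a t distribution with 43 df. It is not at issue here.

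**1. What the coefficient estimates.** For person i at visit t (0 before, 1 after), with collagen C, desmin D and gender G, the model as written is

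Y_it = a + b_C·C_i + b_D·D_i + d·t + g·G_i + u_i + e_it.

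The difference is Y_i1 − Y_i0 = d + (e_i1 − e_i0), which contains neither C nor D. So b_C and b_D come from the person means alone. If the true baseline slope on desmin is β and the true slope of the change is δ, then b_D estimates β + δ/2. Simulation agrees:

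- β=0.5, δ=0: mean coefficient 0.50.
- β=0, δ=0.5: mean coefficient 0.25.
- β=−0.25, δ=0.5: mean coefficient 0.00.

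**2. Baseline correlation implied by Section 2.2.** r = t/√(t² + n − 2), taking n=30 (the size of Group 1; neither correlation's n is stated).

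- Collagen, p=0.0322: t=2.254, so |r| = 2.254/√(5.081 + 28) = 0.39.
- Desmin, p=0.0001 as the bound: t=4.530, so |r| = 4.530/√(20.52 + 28) = 0.65. The true figure is at least this if n=30.

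Both are for CD4 numbers. No figure is given for CD8 function.

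**3. Rejection rate of the planned desmin test when change is unrelated to LN damage.** Inputs from the plan: n=46, two biopsies, two-sided alpha 0.01. Assumptions: within-person correlation (ICC) 0.5-0.7, collagen-desmin correlation −0.5, LN measures constant within person. With 46 − 4 = 42 df the critical t is 2.70.

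SE = √{(1 − r²)(1 + ICC)/2 ÷ [46 × (1 − 0.25)]}

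- r=0.30, ICC 0.5: √(0.91 × 0.75/34.5) = 0.141; 0.30/0.141 = 2.13; rejection about 29%.
- r=0.30, ICC 0.7: √(0.91 × 0.85/34.5) = 0.150; ratio 2.00; about 24%.
- r=0.65, ICC 0.5: √(0.5775 × 0.75/34.5) = 0.112; ratio 5.80; about 99% or more.
- r=0.65, ICC 0.7: √(0.5775 × 0.85/34.5) = 0.119; ratio 5.45; about 99% or more.

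**4. Simulation under the same assumptions.**

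| Baseline desmin r | Desmin-change r | Planned desmin main effect | Desmin × before/after |
|---|---|---|---|
| 0 | 0 | about 1% | about 1% |
| 0.30 | 0 | 24-29% | about 1% |
| 0.64 | 0 | about 99% | about 1% |
| 0 | 0.5 | 11-22% | 70% |
| +0.3 | −0.5 | 1-2% | about 70% |

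A second set-up, with baseline slopes of 0.3, 0.5 and 0.7 residual SD per SD of log desmin, gives 25%, 70% and 95% for the planned test and 0.8-1.2% for the interaction. Fitted mixed models at slope 0.5 give 69% against 1.3%.

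**5. Collagen with desmin in the model.** With collagen r=−0.39, desmin r=0.65 and −0.5 between them, the partial correlation of collagen is

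(−0.39 + 0.65 × 0.5)/√[(1 − 0.4225)(1 − 0.25)] = −0.065/0.658 = −0.10.

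The collagen test then rejects about 4%, so the inflation falls on desmin.

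**6. The interaction test when nodes differ.** The two biopsies come from opposite sides, so baseline LN measures and baseline T cells share a node that the later T cells do not. If 30% of LN-measure variance is node-specific, the interaction rejects about 5-7% with no vaccine effect; at 50%, about 13-20%. The planned main effect rejects 80-96% in the same set-up. A harsher construction at r=0.65 gives 11-19% and 35-65% for the interaction. The node-specific shares are assumptions, and the size depends strongly on how the sharing is modelled.

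**The case against.** The strongest reply concerns 9.4.3. Its outcome is not named, and it could be change from baseline at several post-vaccination visits, with time as a covariate. That would be a coherent mixed model for the stated null. Two details favor it: the lymphoid-tissue CD4/CD8 model in 9.4.3 drops measurement time and uses before/after status, while the CD8-function model keeps time; and the objectives table in Section 3 names no tissue for T-cell function. Against it, the synopsis places CD8 function in lymphatic tissue, where two biopsies yield one change per person and leave no use for a random effect or a time term. The 9.4.3 text is therefore ambiguous, not shown to be wrong. Section 9.4.9 has no such ambiguity.

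Other limits stand:

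- A reader might infer that pre-existing depletion would be reported as an impaired vaccine response for CD8 function too. The documents do not support this. Section 3 asserts CD8 depletion without a figure, and no baseline link is given for IFN-gamma, TNF-alpha or IL-2.
- A reader might apply the 0.39 to desmin. It comes from the collagen p-value, and step 5 shows that the collagen coefficient is little affected.
- No alpha is stated for 9.4.9; using 0.01 there is an assumption.
- Neither section says that the LN measures are baseline values. If values from both biopsies enter, the coefficient mixes between- and within-person association. The simulations do not cover that case, and such a coefficient still does not test baseline damage against later change.

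Permutation p-values do not help, because the coefficient being permuted is still the one for level. Nor can the interaction be taken as implied, since the titer-decay model spells one out.

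**Conclusion.** The point holds for Section 9.4.9: a stated interest in change is tested by a coefficient for average level. It holds for 9.4.3 only if the outcome there is the repeated level. For CD4 populations, the desmin coefficient could be significant with no link to vaccine response, at the rates in steps 3 and 4. Those rates rest on the assumed ICC, collagen-desmin correlation, person-level LN measures, alpha 0.01 and n=30 behind the desmin correlation. For CD8 function the planned test keeps its level if the baseline correlation is zero, and that correlation is unknown. The affected analyses are one secondary and one exploratory. The change is worth making because the present model does not answer the stated question, but it is not a threat to the trial's main result.

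**What to change.** In Sections 9.4.9 and 9.4.3:

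1. Name the outcome and, for 9.4.3, the tissue and visits.
2. Use pre-vaccination collagen and desmin as the LN measures.
3. Add LN measure × vaccination status (before/after) and gender × vaccination status. With two biopsies this equals regressing the post-minus-pre difference on baseline LN measures and gender. Without the gender product, gender cancels from the difference and the equivalence fails.
4. Test the LN interaction as the 9.1 change hypothesis, and base the permutation p-value on that term.
5. Report the LN main effect separately, labelled as association with T-cell level.
6. State the alpha that applies to 9.4.9.
7. Note as a limitation that the two biopsies are different nodes, so node-specific variation shared by baseline LN measures and baseline T cells can bias the change test.

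The cost is SAP wording and a few model terms on data already planned, with no change to conduct. The change test will not inherit the significance that a level association would bring, and item 7 means it is improved but not free of bias.
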